## SYNOPSIS

Principal Investigator	[name] [name], Mater University Hospital, University College Dublin, Ireland
Title	Management and Outcome after Perioperative Care among European Diabetic Patients (MOPED)
Short Title	MOPED
Trial Registration	NCT04511312
Protocol Version	V 1.0
Background & Rationale	
Diabetes is common (about 20m patients in Europe), and patients have more surgical interventions than the general population. There are plausible pathophysiology and clinical mechanisms that diabetic patients are at increased risk of postoperative complications. When postoperative complications occur in the general population, they increase one-year mortality or major adverse events up to one year later. This is likely to be worse in diabetic patients. There is variation in practice guidelines in different countries in the perioperative management of diabetic patients undergoing major surgery, and whether this may affect postoperative outcome has not been investigated on a large scale. Neither is it known whether postoperative outcome differs depending on subgroups of diabetic patients, particularly whether different strata of preoperative glycaemic control affects outcome. If confirmed in this study, personalised perioperative management of diabetic patients may be enabled.

Objectives	
Main Objectives: To conduct the first major European epidemiological study on the perioperative management of diabetic patients undergoing surgery and their 30-day postoperative patient-centered outcome;
 
To evaluate subgroup outcomes, particularly strata of preoperative glycaemic control.
 
Specific Objectives: To address the following research questions: 1. What is the epidemiology of diabetic patients undergoing surgery across Europe: Are there major variations in perioperative glycaemic control? Does management practice vary between centres and between nations? 2. What is the extent and patient-centered impact of postoperative complications among diabetic patients up to 30 days after surgery in Europe? 3. To undertake sub-group analysis comparing these outcomes among *Diabetes Mellitus Type 1, Diabetes Mellitus Type 2, and other diabetic patients; *Patients with different strata (levels) of glycaemic control, i.e. HbA1c <53, HbA1c 53-69 and HbA1c >69 mmol.mol; *Patients who received different anaesthetic techniques: -Volatile versus total intravenous anaesthesia; regional versus general anaesthesia (GA) and

	*Diabetics of longer duration have higher risk of intraoperative hypotension due to autonomic neuropathy.
Outcomes	
Primary endpoint: Days at Home at 30 days after surgery (DAH-30)
 
Secondary endpoints: Comprehensive Complications Index (CCI) score, Quality of Recovery (QoR-15) Day 1 if applicable, 30-day mortality, Length of Hospital Stay, Incidence of specific major adverse events (as listed exhaustively see Appendix 11 'Definitions of Outcomes')
 
Tertiary endpoints: Time to resumption of normal diabetes therapy (insulin or oral hypoglycaemics and diet), Incidence of Diabetic Ketoacidosis or Hypoglycaemia, Incidence and duration of use of IV Insulin Infusion Therapy, Change in diabetic management at 30 days
 
Intraoperative and postoperative management techniques of diabetes therapy will be documented, including capillary blood glucose levels before, during and <2hr after surgery.

Inclusion & Exclusion Criteria	
Inclusion criteria: Diabetic patients aged 18 years or over (all classes except gestational diabetes) undergoing surgery (defined as requiring any general anaesthesia technique or any specific regional anaesthetic technique or a combination). Ambulatory, elective or emergency surgery and patients who receive postoperative care in intensive care or high dependency units will be included. Pre-defined subgroups of diabetic patients will be highlighted for later analysis.
 
Exclusion criteria: Patients who are not diabetic; Patients with gestational diabetes; Patients undergoing minor surgery, i.e. surgery under local anaesthetic infiltration alone with or without monitored sedation alone or surgery not as defined in the inclusion criteria above.

Project Measurements	
Patients' consent will be requested to allow documentation of their perioperative course and 30-day outcome as outlined in the outcome measures.
 
Apart from routine clinical care, no intervention is planned.

Number of Participants	5,000
Duration	In each participating centre, recruitment of new patients will continue for a period of 12 months after their registration with ESAIC as a participating centre, until the target 5,000 patients is reached. Follow up duration to 30 days after surgery.
Centres	This will be an international, multicentre prospective observational study. Any centre where colleagues can enrol and collect the data outlined in a minimum of n=45 patients are welcome to participate.

Statistical Considerations	
Up to 5% of the population of Europe is thought to have diabetes. About 30m surgeries are performed in Europe per annum, therefore perhaps 1.5m diabetics have surgery in Europe per annum. It is proposed to evaluate a pragmatic sample of 5,000 European diabetic patients across at least 50 centres in a minimum of 10 nations.
 
Centres undertaking surgery for diabetic patients will be invited to contribute patients. It is envisaged that this target number would be enrolled over a two-year period from initial roll-out, with up to a further 12 months needed for final data acquisition, cleaning and analysis.
 
A sample size of 5,000 should be sufficient to avoid over-fitting and variance inflation for up to 63 factors or interactions. In addition, a sample size of 5,000 will have 90% power to find a small standardised difference of 0.10 as significant at <math>P < 0.05</math> for up to 63 independent hypotheses in comparing subsets of interest.

Risk-Benefit analysis	
There is no risk to patients participating in this study other than any risk associated with their perioperative care. Individual patients will not benefit from the study, but the knowledge gained from the overall evaluation will inform best practice in this previously under-researched field.

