## 7. STATISTICAL METHODOLOGY

### 7.1 Sample size estimation

It is proposed to evaluate a pragmatic sample of 5,000 European diabetic patients across at least 50 centres in a minimum of 15 nations. It is expected that this should be sufficient for the main epidemiological aspects of this study. It is envisaged that this target number would be enrolled over a two-year period from initial roll-out, with up to a further 12 months needed for final data acquisition, data cleaning and analysis. A sample size of 5,000 should be sufficient to avoid over-fitting and variance inflation for 50 to 70 factors and interactions based on the conventional square root or 100 values per variable respectively. In addition, a sample size of 5,000 will have at least 90% power to find a small standardized difference of

0.15 as significant at  $P < 0.05$  (Bonferroni corrected at  $P < 0.0007$ ) for up to 70 independent hypotheses and in comparing subsets of interest.

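### The Synopsis claims 90% power for a standardised difference of 0.10 over 63 hypotheses; after correction 5,000 patients give about 57% at best, and Section 7.1 states a different basis (0.15, 70 hypotheses)

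*Protocol*

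**What the plan says.** Two places in the protocol give the power of the same sample.

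- **Synopsis, Statistical Considerations:** the power statement reads "a sample size of 5,000 will have 90% power to find a small standardised difference of 0.10 as significant at". The level given is P < 0.05, and the scope of the claim is "for up to 63 independent hypotheses in comparing subsets of interest". No multiplicity correction and no per-test significance level is named.
- **Section 7.1, Sample size estimation:** the corresponding statement opens "In addition, a sample size of 5,000 will have at least 90% power to find a small standardized difference of". The difference named there is 0.15. The level is again P < 0.05, but with a Bonferroni threshold of P < 0.0007, and the scope of the claim is "for up to 70 independent hypotheses and in comparing subsets of interest".

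Neither place says whether tests are one- or two-sided, or how the 5,000 patients are assumed to divide between the subsets compared.

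The surrounding text also differs. The Synopsis reads "It is proposed to evaluate a pragmatic sample of 5,000 European diabetic patients across at least 50 centres in a minimum of 10 nations", whereas Section 7.1 gives a minimum of 15 nations. The Synopsis allows up to 63 factors or interactions in the models; Section 7.1 gives 50 to 70.

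**The concern.** The effect size, the number of hypotheses and the treatment of multiplicity all differ between the two statements, although the sample is the same. The Synopsis claims the smaller detectable difference and mentions no correction for its 63 hypotheses.

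Subgroup comparisons (diabetes type, HbA1c stratum, anaesthetic technique) are among the stated objectives, so readers will use the power statement to interpret them. Someone relying on the Synopsis could take a null subgroup result as good evidence against a difference of 0.10, when under the correction in Section 7.1 the study would miss such a difference nearly half the time even in the most favourable split.

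**Working it through.** **Inputs from the protocol.** N = 5,000. Synopsis: difference d = 0.10 (SD units), power 90%, P < 0.05, 63 hypotheses. Section 7.1: d = 0.15, power at least 90%, P < 0.0007, 70 hypotheses.

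**Assumptions, because the protocol is silent.** Two-sided tests, a 1:1 split (the most favourable), independent patients, no missing data.

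**Formula.** For a two-group comparison with a share p of patients in the smaller group, power ≈ Φ(d·√(N·p·(1−p)) − z), where z is the two-sided critical value. At p = 0.5, √(5,000 × 0.25) = √1,250 = 35.36.

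**1. The Synopsis figure.** d·√1,250 = 0.10 × 35.36 = 3.536.

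| Per-test level | z | Power for 0.10 |
|---|---|---|
| 0.05, uncorrected | 1.960 | Φ(1.576) = 94.2% |
| 0.05/63 = 0.00079 | 3.355 | Φ(0.181) = 57.2% |
| 0.0007 (Section 7.1) | 3.390 | Φ(0.146) = 55.8% |

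The stated 90% is met only without correction. With Bonferroni it survives two tests (90.2%) but not three (87.3%).

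**2. Other readings of the Synopsis.** At 0.05/63 the noncentral t distribution gives 57.1%; the Šidák level gives 57.4%; one-sided testing gives 64.7%. Taking 5,000 as the size of each group gives 95.0%, but that contradicts the stated total.

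**3. The Section 7.1 figure.** 0.15 × 35.36 = 5.303, and Φ(5.303 − 3.390) = 97.2%. The claim of at least 90% is correct at 1:1. The threshold also agrees with its source: 0.05/70 = 0.00071.

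**4. What 5,000 patients can detect with 90% power.** d = (z + 1.2816) × √(2/2,500). At 0.05/63: 4.637 × 0.02828 = 0.131. At 0.0007: 4.671 × 0.02828 = 0.132. For d = 0.10 at 0.05/63, the total needed would be 4 × 4.637² / 0.01, or about 8,600.

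**5. Unequal subsets.**

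| Split | 0.10 at 0.05 | 0.10 at 0.05/63 | 0.15 at 0.0007 |
|---|---|---|---|
| 50:50 | 94.2% | 57.2% | 97.2% |
| 30:70 | 90.0% | 45.4% | 92.9% |
| 20:80 | 80.7% | 29.9% | 80.3% |
| 10:90 | 56.4% | 10.9% | 41.8% |

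For d = 0.15 at 0.0007, 90% power requires 5,000 × p(1−p) × 0.0225 ≥ 4.671² = 21.82. So p(1−p) ≥ 0.194 and p ≥ about 0.263, roughly 1,320 patients in the smaller subset.

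**6. If the 63 tests were left uncorrected.** With all 63 null hypotheses true, the chance of at least one false positive is 1 − 0.95^63 = 96%, and the expected number is 63 × 0.05 = 3.15.

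**7. The hypothesis counts.** Section 7.1 names two rules of thumb for the number of model factors, the square root of the sample size and 100 values per variable. They give √5,000 = 70.7 and 5,000/100 = 50. The 70 hypotheses match the first. Neither rule gives 63 from 5,000.

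**The case against.** The Synopsis does not say that its P < 0.05 is corrected. Read as a per-test level its figure is true: 94% at 1:1, and about 90% at 30:70. The Section 7.1 figure is also true at 1:1, so as arithmetic the two sentences can both stand, and the 57% appears only once a correction is read into the Synopsis. Moreover, the sample is described as pragmatic, the main analysis in Section 7.3.1 is descriptive, and the power statement is an addition to the sample size and not its source. Section 7.1 already shows the correction and a figure that reproduces.

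Part of this stands. The sample size does not rest on the Synopsis figure, and nothing about enrolment or data collection is affected. The 96% false-positive risk describes an uncorrected analysis, which is not what Section 7.1 indicates. Also, 63 factors lie inside the range of 50 to 70, so that difference is one of wording.

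The uncorrected reading does not rescue the sentence. It offers its power for up to 63 independent hypotheses, and Section 7.1 applies Bonferroni to the same kind of claim. A reader cannot hold 90% power for 0.10 and the protocol's own threshold together.

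**Conclusion.** The concern holds. The Synopsis states a power that 5,000 patients do not deliver under the correction in Section 7.1, and the two places give different bases for the same sample. For a difference of 0.10, power is about 57% at 0.05/63 and 56% at 0.0007, against the stated 90%. The difference detectable with 90% power is about 0.13.

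These figures rest on two-sided testing, an equal split of all 5,000 patients, complete data and no allowance for clustering within centres. They are best-case values with respect to the split. One-sided testing would raise the 57% only to about 65%. A statistical analysis plan could not resolve this, because the conflict lies between two current statements in the protocol.

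**What to change.** Replace the power sentence in the Synopsis with the basis of Section 7.1: a standardised difference of 0.15, a Bonferroni threshold of P < 0.0007, up to 70 hypotheses, and at least 90% power. In both places add the assumptions: two-sided tests (if that is intended), and 90% power only where the smaller subset holds at least about 26% of the 5,000 patients. Without that qualifier, moving the 0.15 into the Synopsis would overstate power for uneven comparisons (80% at 20:80, 42% at 10:90).

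If the sponsor prefers to keep 0.10 in the Synopsis, it should state that power after correction is about 57% at an equal split.

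In the same edit, reconcile the minimum number of nations (10 or 15) and use one wording for the number of model factors. Section 13 lists a Protocol Synopsis as Appendix 1; if it carries the same sentence, change it there too.

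The cost is one paragraph in the Synopsis and one qualifying sentence in Section 7.1. The stated detectable difference becomes less favourable. No extra patients or data are needed.

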## List of Abbreviations

AKI	Acute kidney injury
ASA classification	American Society of Anaesthesiologists Physical Status classification system
CCI	Comprehensive Complications Index
CRF	Case report Form
CTN	Clinical Trial Network
CVA	Cerebrovascular accident
DAH-30	Days at home at 30 days
DVT	Deep vein thrombosis
eCRF	Electronic Case Report Form
ESAIC	European Society of Anaesthesiology and Intensive Care
GA	General anaesthesia
ICF	Informed Consent Form
ICH-GCP	International Council for Harmonisation - Good Clinical Practice
ICU	Intensive care unit
IRB	Internal review board
MI	Myocardial infarction
MINS	Myocardial injury after noncardiac surgery
NC	National Coordinator
PE	Pulmonary embolism
PI	Principal Investigator
PIS	Patient Information Sheet
PPC	Postoperative pulmonary complication
QoR-15	Quality of Recovery 15

SAE	Serious adverse event
SC	Steering committee
SOP	Standard operational procedure
SORT	Surgical Outcome Risk Tool
SSI	surgical site infection

## 2. ETHICAL AND REGULATORY ASPECTS

### 2.1 Ethical Conduct of Study

The research project will be carried out in accordance to the research plan and the principles enunciated in the current version of the Declaration of Helsinki (amendment 2013) by the World Medical Association and the ICH-GCP Guidelines E6(R2). Specific national and local regulatory authority's requirements will be followed as applicable.

### 2.2 Risk categorisation

MOPED is a prospective cohort study asking patients to assent to documentation of their perioperative clinical course and progress, and a 10 minute follow-up telephone call, if discharged, at 30 days post surgery. No research related interventions are anticipated and all patients will receive routine care according to the standards laid out in each institution.

### 2.3 Institutional Review Board (IRB) and Competent Authorities (CA) or equivalent

In all cases, prior to study initiation, the local Principal Investigator (PI) at each centre must submit the study documents to the responsible IRB or equivalent for ethical judgment and obtain document of proof that the study has been subject to IRB review and given approval/favourable opinion and exemption of patient consent if applicable.

If informed consent is not required by the local IRB, an explicit, written exemption must be obtained from the IRB. No substantial changes will be made to the protocol without prior IRB approval, except where necessary to eliminate apparent immediate hazards to study participants.

In the unlikely event of premature study end or interruption of the study, a report will be sent to the IRB within 15 days, or as required. The regular end of the study is reported to the IRB within 90 days, the final study report shall be submitted within one year after study end, , or as required. It is the local PI responsibility to communicate with their local IRB within their local timelines.

#### 2.4 Participant Information and Informed Consent

Written, informed consent, using the approved Informed Consent Form (ICF), will be sought from each patient prior to inclusion unless an explicit, written exemption by the responsible IRB is provided. Patient Information Leaflet (PIL) and any other written information to be provided to the patients as well as advertisement for subject recruitment (if used) must be subject to IRB review and given approval/ favourable opinion.

If applicable, patients' consent will be sought as follows: Prior to surgery, the patients will be presented with the IRB-approved PIL providing information for participant to make an informed decision about their participation in the study, i.e. explaining the nature of the study, its purpose, the general lack of any procedures involved, the expected duration, the potential risks and benefits and any discomfort participation may entail. (see Appendix 2 Patient Information Sheet, Appendix 3 Patient Informed Consent Form).

Each participant will be informed that their participation in the study is voluntary and that he/she may withdraw from the study at any time and without explanation, that withdrawal of consent will not affect his/her subsequent medical assistance and treatment and that no further data will be collected, while already collected, encoded data will be pseudonymised and analysis may be performed up to the point of data collection.

The participant will be informed that his/her medical records will be examined by authorised individuals other than their treating physician. The participant will read the statement and will have the opportunity to ask questions before signing and dating the ICF, and will be given a copy of the signed document. Patients will confirm that they were given adequate time to reach a decision. The ICF must also be signed and dated by the investigator (or designee) and it will be retained as part of study records.

Diabetic patients listed for both elective and emergency surgery will be approached by a member of the research team and invited to participate.

While for elective patients, consent may be obtained in a preoperative clinic up to 90 days prior, for emergency surgery diabetic patients' consent may be requested on the ward, immediately prior to coming to theatre on the day of surgery and up until hospital discharge.

There is even less knowledge currently about the management and outcomes of diabetic patients undergoing *emergency* surgery, who are acknowledged to be a particularly high-risk group, compared to diabetic patients undergoing elective surgery. Therefore, including a cohort of these patients is particularly important to evaluate risk factors for adverse outcomes which may be mitigated. There is also anecdotal evidence that practice of managing these patients varies widely between nations and individual centres.

The only difference from normal care will be the 10 minutes phone call follow-up at 30 days post surgery. If patients are still in hospital on Day 30, this 30 day data may be collected on

the ward. Patients in hospital overnight will be asked to give their responses to the Quality of Recovery score (QoR-15) Day 1 postoperative only, which takes 3-5 minutes.

The sponsor provides templates of the Patient Information Sheet and Consent Form in English. (See appendices). All translations and adaptation of the Appendices should be sent to ESAIC (the sponsor) for validation. SOP and guidance published by the Sponsor should be followed in this regard.

### 2.5 Participant privacy

The investigator affirms and upholds the principle of the participant's right to privacy and shall comply with applicable privacy laws. Specifically, anonymity of the participants shall be guaranteed when presenting the data at scientific meetings or publishing them in scientific journals.

Individual subject medical information obtained as a result of this study is considered confidential and disclosure to third parties is prohibited. Subject confidentiality will be further ensured by utilising subject identification code numbers and only pseudonymised data will be recorded in the central database.

For data verification purposes, authorised representatives of the sponsor or an ethics committee may require direct access to parts of the medical records relevant to the study, including participants' medical history.

### 2.6 Early termination of project

MOPED is an observational cohort study. Therefore, premature termination of the study resulting from ethical or safety concerns is most unlikely. In case of insufficient participant recruitment, the study period may be extended to reach the calculated sample size of 5,000 patients.

### 2.7 Amendments, Changes

Only the steering Committee (SC) or persons delegated by the SC are entitled to amend the protocol. National Coordinating Investigators and Local Principal Investigators (PI) will receive timely notification of changes and will be required to submit amendments locally. Written documentation of the amendments' approval will be provided to the sponsor and substantial amendments of the protocol will be only implemented after approval of the responsible IRB.

In consideration of the observational nature of the study, the necessity of protocol deviations to protect the rights, safety and well-being of human subjects without prior approval of the sponsor and the IRB appears remote. Such deviations must be documented and reported to the sponsor and the IRB as soon as possible.

All non-substantial amendments like administrative changes will be communicated to the IRB as necessary by the PI. It is the local PI responsibility to communicate with their IRB.

### 2.8 Background

The incidence of diabetes is increasing globally, including within Europe. There is an estimated 20million diabetic patients in Europe, which is likely to increase, thereby adding to societal demands on European health services.[1] Diabetic patients are more likely to have surgical interventions than the general population.[2] There are plausible pathophysiology and clinical mechanisms that diabetics are at increased risk of postoperative complications.[3,4] When postoperative complications occur in the general population, they increase mortality or increase risk of major adverse cardiovascular events (Myocardial

Infarction, Cerebrovascular Accident, Pulmonary embolism) at 30-days and up to one year later.[5-7] In addition, diabetes is an independent risk factor for surgical site infections [6].

There is variation in practice guidelines in different countries in the perioperative management of diabetic patients undergoing major surgery, but this has not been documented on a large scale.[3,7,8] Given the multiplicity of guidelines and differing recommendations, it is unsurprising that variability of 'real-world' clinical practice with regard to perioperative management of oral antihyperglycemic medications and insulin therapy has been noted in audits such as the National Confidential Enquiry into Patient Outcome and Death (NCEPOD).[9]

Further, although it is recognised that diabetic patients are at increased risk of postoperative complications[5-8], this has not been recently evaluated, especially in light of ongoing developments in perioperative care, such as Enhanced Recovery Programmes.[7] While a quality improvement intervention study has shown that maintaining tight preoperative glycaemic control improves postoperative glycaemic control[8], it is not known if this reduces postoperative morbidity overall. Further, whether certain anaesthetic techniques may be associated with better or worse outcomes after major non-cardiac surgery is unknown.

